### 7.1.2 Physical Examination

**Physical examination**, including assessment of general appearance, skin, head, and neck (including eyes, ears, nose, and throat), lymph nodes, thyroid, musculoskeletal/extremities, cardiovascular system, lungs, abdomen, and neurological status as well as the fractured limb and the administration site will be performed preferably by the same person (Principal Investigator).

**Height** (without shoes) will be measured in centimetres (cm). Weight (without shoes) will be measured in kilograms using a scale. Historical patient information and/or patients reports must not be used.

**Body Mass Index** (BMI) will be calculated as follows: Weight (Kg)/Height (m) = BMI.

### 7.1.3 Laboratory Safety Measurements

The blood collected for biochemistry, haematology, and serological testing will be done at the Investigator's laboratories.

The total amount of blood collected [REDACTED]

[REDACTED] during the whole study is expected not to exceed 300 ml.

Table 7: Overview of Blood Collection

██████████	██████████	██████████	██████████
██████████	████████████████	██████████	██████████
██████████	██████████	██████████	██████████
██████████	██████████	██████████	██████████
██████████	██████████	██████████	██████████
██████████	██████████	██████████	██████████
██████████	██████████	██████████	██████████
██████████	████████████████	██████████	██████████
██████████	██████████	██████████	██████████
██████████	██████████	██████████	██████████
████████████████			

### Serology

████████████████
████████████████
████████████████
████████████████
████████████████
████████████████
████████████████

For this analysis, 9 ml of blood will be collected and the analysis will be performed at the local laboratory.

### Safety

Laboratory tests will be performed

████████████████
████████████████

**ALLOB-DU1 - Clinical Study Protocol**

ALLOB-DU1 CSP V 05 Author: [name] February 02, 2017 Pg. 73/136

The following parameters will be analysed as safety measurements:

For these analyses, 11 ml of blood will be collected at each visit.

These analyses will be performed at the local laboratory.

### Other exploratory Analyses:

In order to assess the effects of treatment

A series of black horizontal bars of varying lengths, likely representing redacted text or data. The bars are arranged in a grid-like pattern, with some bars being significantly longer than others, suggesting a list or table where some entries are much larger than others.

For these analyses, 29 ml of peripheral blood will be collected in 4 different blood collection tubes (3×9 ml and 1×2 ml) [REDACTED]

---

---

**ALLOB-DU1 - Clinical Study Protocol**

ALLOB-DU1\_CSP | V 05 | Author: [name] | February 02, 2017 | Pg. 74/136

## 7.2 Other Safety Measurements

### 7.2.1 Women with childbearing potential

Women with childbearing potential must use a reliable method of contraception for at least 6 weeks prior to study inclusion (screening visit) and during the whole study period. Reliable contraceptive methods include orally administered hormonal contraceptives, surgical intervention (e.g., tubal ligation), and intrauterine device (IUD).

Moreover, women with childbearing potential will systematically undergo urine pregnancy testing at each visit performed at the Investigating site (from Screening up to month 6). Pregnancy test kits will be provided by the Sponsor, performed on site according to manufacturer's instructions, and results will be recorded in the CRF.

### 7.2.2 Additional safety examinations and procedures

If any unclear clinical event, including symptoms, signs, or other observations or abnormalities, should occur, the Investigator, or any other physician in charge, may perform additional clinical examinations and procedures (other than outlined in this protocol), including any clinical, laboratory, imaging and/or technical testing, in order to clarify and establish the aetiology and diagnosis of this clinical event.

X-ray of the thorax and liver Ultra Sound will be performed at 6 months after treatment █ in order to confirm absence of any ectopic mineralization.

## 8 ADVERSE EVENTS AND SERIOUS ADVERSE EVENTS

### 8.1 Definitions

#### 8.1.1 Adverse Event (AE) and Serious Adverse Event (SAE)

- An adverse event (AE) is any untoward medical occurrence in a patient or clinical investigation subject who has been administered a pharmaceutical product and/or any investigational medicinal product and which does not necessarily have a causal relationship with this treatment. An AE can therefore be any unfavourable and unintended signs (including any abnormal laboratory findings), symptoms, or disease temporally associated with the use of a medicinal product, without any judgment about causality.
- All AEs will be reported from the time a signed and dated ICF is obtained until completion of the subject's last visit.
- Events related to pre-existing conditions should be reported as AE, upon Investigator's judgement, justified by an increase in frequency or intensity of signs or symptoms.
- Adverse events will be graded with respect to intensity and classified as either serious or non-serious according to the World Health Organisation Classification

**Table 8: Classification of Adverse Events**

Intensity	Mild	Some awareness of symptoms or signs that does not interfere with the patient's usual activities or is transient, easily tolerated and resolved without treatment and with no sequelae
	Moderate	Symptoms or signs causing enough discomfort to interfere with the patient's usual activities, and/or requires symptomatic treatment
	Severe	Incapacitating event, including symptoms or signs, causing severe discomfort and inability to work or to perform usual activities, and requires treatment
Seriousness	Serious (SAE)	
Any untoward medical occurrence that at any dose:
 
 
– Results in death, or
 
– Is life-threatening, or
 
– Requires subject hospitalization or prolongation of existing hospitalization, or
 
– Results in persistent or significant disability/incapacity, or
 
– Is a congenital anomaly / birth defect
 
– Is medically important (see note 3)
 

	Non-serious	Any other adverse event

**Notes**

1. The term "life-threatening" in the definition of SAE refers to an event in which the patient is at immediate risk of death at the time of the event; it does not refer to an event, which hypothetically might have caused death if it was more severe or had continued untreated. The term "life-threatening" does not imply a possible future course which might or might not have happened, but was prevented due to adequate physician's action. For example, a simple bacterial wound infection can potentially lead to gangrene, sepsis, and eventually death; while sepsis is usually regarded as a SAE because of known high mortality, the primary wound infection itself is usually not regarded as a SAE. In analogy, a newly diagnosed malignant disease is usually regarded as a SAE because malignant diseases usually have a high mortality rate and are therefore life-threatening.

## ALLOB-DU1 - Clinical Study Protocol

ALLOB-DU1_CSP	V 05	Author: [name]	February 02, 2017	Pg. 77/136
---------------	------	-------------	-------------------	------------

2. To ensure no confusion or misunderstanding of the difference between the terms "serious" and "severe", which are not synonymous, the following clarification is provided: the term "severe" is often used to describe the intensity (severity) of a specific event (as in mild, moderate, or severe myocardial infarction); the event itself however may be of relatively minor medical significance (such as severe headache). This is not the same as "serious," which is based on patient/event outcome or action criteria usually associated with events that pose a threat to the patient's life or functioning.

3. In addition, events that may not meet the criteria indicated above, but which the Investigator finds very unusual and/or potentially serious, will be reported as SAE. Indeed, medical and scientific judgments should be exercised in deciding whether reporting is appropriate in other situations, such as important medical events that may not be immediately life-threatening or result in death or hospitalization but may jeopardize the patient or may require intervention to prevent one of the other outcomes listed in the definition above. These events should also usually be considered as SAEs. Examples of such events include intensive treatment in the Emergency Room or at home for allergic bronchospasm, blood dyscrasias or convulsions that do not result in hospitalization, and/or development of drug dependency or drug abuse.

4. Some medical events may jeopardise the subject or may require an intervention to prevent one of the characteristics/consequences described in the SAE definition (Section 8.1). Such events (referred as "important medical events") should also be considered as "serious" in accordance with the definition.

5. Elective procedures requiring hospitalization will not be considered as SAEs if they were pre-planned prior to signing ICF (as documented in source documents). However, complications or other events that may occur during hospitalization will be considered as AEs or SAEs and will be captured accordingly.

#### **8.1.2 Causal relationship with the Investigational Medicinal Product**

Causality shall be determined according to the definition of an adverse reaction (Section 8.1).

All adverse events judged by either the Investigator or the Sponsor as having a reasonable suspected causal relationship to an investigational medicinal product qualify as adverse

## ALLOB-DU1 - Clinical Study Protocol

ALLOB-DU1_CSP	V 05	Author: [name]	February 02, 2017	Pg. 78/136
---------------	------	-------------	-------------------	------------

reactions. The causality assessment given by the Investigator should not be downgraded by the Sponsor. If the Sponsor disagrees with the Investigator's causality assessment, both, the opinion of the Investigator and the Sponsor should be provided with the report.

Determination of the causal relationship between an AE/SAE and the trial medication must be made by the Investigator by answering the question: "Is the causal relationship between the medicinal product and this AE/SAE reasonably possible?" on the following basis

- Yes: Certain
- Likely
- Unlikely
- No: Not related
- Unknown/ Not assessable

Indeed, causality assessment is a clinical decision based on all available information at the time of and after the occurrence of the event. The factors which may be considered when evaluating the causal relationship of an AE/SAE to the IMP administration include the followings:

- Underlying, concomitant, and/or intercurrent disease(s): each report should be evaluated in the context of the natural history and course of the disease being treated and any other diseases the patient may have had prior to, or developed during the course of the study
- Concomitant medication or treatment: other drugs the patient is taking or treatment the patient is receiving at the time of the event should be examined to determine whether any of them may be recognized to cause the event in question
- Known response pattern for this class of drug
- The pharmacology and pharmacokinetic of the IMP: absorption, distribution, metabolism, and excretion of the IMP or other medications the patient is receiving coupled with the pharmacodynamic responses should be considered when evaluating an event

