**8.2.3 Summary of Adverse Drug Reactions and Possible Risks related to the Product and/or to the Procedures**

There is no reported ADR with ALLOB® at this stage.

However, PREOB®, an autologous osteoblastic cell product, has been administered in humans in phase I/IIa and IIb studies. A summary of observed adverse events possibly related to study treatment (i.e., PREOB® and/or the implantation procedure) is listed in Table 11.

**Table 11: Summary of Observed Adverse Events (AE) and Serious Adverse Events (SAE) possibly related to Study Treatment (i.e., PREOB® and/or the Implantation Procedure)**

Non-Serious AE		SAE (Non-Fatal)	
Total	27.0%	Total	3.2%
Pyrexia	7.9%	Systemic inflammatory response syndrome	1.6%
Pain	17.5%	Pancytopenia**	1.6%
Pain (general disorders)	6.3%	Pyrexia**	1.6%
Procedural Pain	4.8%	Altered status of consciousness**	1.6%
Musculoskeletal Pain	3.2%		1.6%
Arthralgia	1.6%		
Pain in extremity	1.6%	Hypotension**	
Urinary retention	1.6%		
Post-procedural haematoma	1.6%		
Post-procedural bleeding	1.6%		

\* AEs and SAEs were limited to TEAEs and STEAEs and reported per Preferred Term (PT) (MedDRA coding), along with their frequency of occurrence in subjects. Subjects were counted once for each PT. An AE/SAE was considered as treatment-emergent if it occurred on or after the date of the IMP implantation. In case of missing start date, the AE was considered as treatment-emergent. \*\* 4 SAEs were reported in the same patient.

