**8.2.4 Assessment of the Safety Monitoring Committee**

A review of all the reported SAE potentially related to the IMP, and especially those related to immunological reactions (severe AESCs), will be done by the Safety Monitoring Committee

(SMC) after the inclusion of each block of 4 patients until the inclusion of the first 16 patients. This review will cover all SAE potentially related to the IMP from the day of treatment to the first 15 days of follow-up for the first block of 4 patients and from the day of treatment to the end of hospitalization period for the second, third and fourth blocks of 4 patients.

The main conclusions and decisions will be communicated to all Investigators 48 hours after each meeting. A report will subsequently be prepared and its summary submitted to the IECs and CAs. The SMC will be composed by a Safety Consultant and one medically qualified member of the Sponsor. This committee will decide whether the study can be continued as planned. If the decision is to stop or modify the study, it will be communicated by the Sponsor to the Investigators of all centres within 48 hours, the IECs and CAs.

After the review of the fourth block of 4 patients, the recruitment will continue (up to maximum 32 treated patients) and no more safety committee will be performed for all the subsequent treated patients. The safety of all patients will be monitored regularly as described in the study protocol and documented as appropriate.

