## ALLOB-DU1 - Clinical Study Protocol

ALLOB-DU1_CSP	V 05	Author: [name]	February 02, 2017	Pg. 85/136
---------------	------	-------------	-------------------	------------

- Criteria for seriousness (death, life-threatening, persistent or significant disability or incapacity, new or prolonged hospitalization, congenital abnormality or birth defect, important medical event), severity (mild, moderate, severe), and frequency (intermittent, continuous, or other)
- Causal relationship with the IMP (assessment of drug-event causal relationship and consistency with applicable product information, e.g., the Investigator's Brochure and evaluated as certain, likely, unlikely, unrelated, unknown or inassessable)
- Causal relationship with the trial procedures, including blood sampling and the product implantation (implantation , surgery, anaesthesia)
- Relationship with the study disease and/or underlying, concomitant, and/or intercurrent diseases, relationship with concomitant medication or treatment, and/or drug interactions
- Any other relevant information

Based on data and information available in both the SAE Form and in the Investigation and Conclusion Report (see below) (and additional queries, if needed), the SSO will notify the occurrence of SUSAR, SAR, and/or SAE related to the trial procedures to both Eudravigilance database and ECs (all Member States concerned), and to all concerned PIs and Sponsor in agreement with all applicable national legislation.

This notification will be sent by the SSO to the ECs and Eudravigilance database, while blinding will be preserved for both the PIs and Sponsor.

SUSARs that are fatal or life-threatening are recorded and reported within 7 days of awareness. Other SUSARs are recorded and reported within 15 days of awareness.

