### 10.9 Safety Follow-up

For the first 16 patients, patients will be treated in the study by sub-group (block) of 4. Before starting the treatment of a new block of 4 patients, a safety review at the end of the Visit #3 for the first block (48 hours of hospitalization and first follow-up visit at 2 weeks after implantation) and at the end of Visit #2 (48 hours hospitalisation or on-site visit) for the other blocks will be conducted. If from this review, 3 or more patients have not experienced SAE potentially related to the IMP, including severe AESC, and resulting in death, life-threatening, resulting in persistent or significant disability/incapacity, requiring intervention to prevent permanent impairment or damage, the next block of 4 patients will be allowed for treatment (Visit #2).

The members of the SMC will perform this safety monitoring analysis.

After inclusion of the first 16 assessable patients and based on 6-month treatment follow-up, a safety and efficacy interim analysis will be planned.

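### The causality scale asks whether a relationship is possible but has no possible grade, and no text ties its grades to the relatedness terms used elsewhere

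*Combined protocol and SAP*

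**What the plan says.** Section 8.1.2 puts one question to the investigator for every AE and SAE: "Is the causal relationship between the medicinal product and this AE/SAE reasonably possible". The answers listed under it are certain (printed after a Yes label), likely, unlikely, then "No: Not related", then unknown/not assessable. Section 8.3.1.2 gives the scale for the SAE form in running prose, "evaluated as certain, likely, unlikely, unrelated, unknown or inassessable", without Yes or No labels.

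Other sections use different relatedness terms:

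- Section 8.2.4, on the SMC: "This review will cover all SAE potentially related to the IMP from the day of treatment".
- Section 10.9, on release of the next block of four: "3 or more patients have not experienced SAE potentially related to the IMP, including severe AESC", followed by a list of serious outcomes.
- Section 10.8: missing data after withdrawal for a treatment-related AE are replaced by WOCF, and other missing data after the last visit by LOCF.
- Section 10.5.7.1: AEs are tabulated by relationship to product or procedure.
- Section 8.2.3, introducing Table 11 for the sponsor's autologous product: "A summary of observed adverse events possibly related to study treatment".

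**The concern.** The question sets its threshold at reasonable possibility, but none of the answers sits at that threshold. The gap falls where this trial most needs resolution. The Synopsis singles out fever and local pain or swelling as possible signs of an immune reaction to the allogeneic cells, while Table 10 lists implantation-site pain and infectious complications as risks of the procedure itself. For such events, possible is often the honest answer.

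Two things are at stake. The first is information: once a possible event is entered as likely or unlikely, the related-AE tables depend partly on how each investigator settles a forced choice. The second is definition: the SMC review, block release and the imputation rule each rest on a relatedness term that is not tied to the grades being collected.

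**Working it through.** The documents give no figure that depends on the causality scale, so there is nothing to reproduce. The check compares the sections and adds a little algebra.

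**1. Is the missing grade an artefact of text extraction?** No. Section 8.1.2 gives the grades as a list and 8.3.1.2 gives them in a sentence. The two agree grade by grade, and neither contains possible.

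**2. Can the lost information be recovered?** Let C, L and U be the numbers of events the investigators would grade certain, likely and unlikely on a scale that included possible, and P the number they would grade possible. Let a, between 0 and 1, be the unknown share of P recorded as likely. Then:

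- recorded likely = L + aP
- recorded unlikely = U + (1 − a)P

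Two observed counts carry four unknowns (L, U, P, a), so P cannot be identified. There are two ways to define related:

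- Certain plus recorded likely gives C + L + aP, which lies anywhere from C + L to C + L + P.
- Adding recorded unlikely gives C + L + P + U, which includes every possible event but also every event judged unlikely.

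No cut-off on the existing scale returns C + L + P, the count of events at or above the threshold the question asks about.

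**3. Do the Yes and No labels supply a mapping?** The list allows two readings:

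- *Each label covers the grades printed after it.* Unlikely then means Yes, and unknown/not assessable means No, so an event nobody could assess is counted as not reasonably possible.
- *Each label belongs only to the grade beside it.* Likely, unlikely and unknown then have no stated Yes or No.

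The indentation was lost when the PDF was read, so the layout cannot decide between them. Section 8.3.1.2 has no labels and does not help. On the first reading unknown becomes unrelated by default; on the second it has no status.

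**4. Are the other terms tied to grades?**

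- Potentially related (Synopsis, 8.2.4, 10.9): no grade is named.
- Treatment-related (10.8): no grade is named.
- Relationship tables (10.5.7.1): no rule for combining grades.
- Adverse reaction (8.1.2, 8.1.3): defined by evidence or argument for causality, again without reference to grades.

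**5. What follows for imputation?** Take a patient who withdraws because of an AE graded unlikely or unknown. Section 10.8 calls for WOCF if that AE is treatment-related and LOCF if it is not. The visible text does not say which applies. The result differs only when the patient's worst and last observations differ.

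**The case against.** The strongest reply is that the list in 8.1.2 is probably a grouped one. If so, certain, likely and unlikely all answer Yes, and a possible event recorded as unlikely still counts as related. That is a fair reading of the printed order, and it weakens any claim that unlikely is wholly unmapped. It does not restore the possible category, and it leaves unknown/not assessable under No.

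The second reply concerns safeguards, and these are real. All AEs are recorded (8.3.1.1). All SAEs are notified within 24 hours, related or not (8.3.1.2). Either the investigator or the sponsor may classify an event as a reaction, and the sponsor should not downgrade (8.1.2). Causality with the trial procedures is recorded separately (8.3.1.2). The DSMB sees all safety data (8.3.4). They limit the harm. However, the DSMB review waits for 6-month results on 16 assessable patients, and between blocks the SMC reviews only SAEs that meet the undefined term.

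A reader might go further and infer that events which ought to stop a block can be graded out of the gates. The documents do not support that. No section filters the SMC review or block release by grade. The phrase used, "3 or more patients have not experienced SAE potentially related to the IMP", is broad and could be applied inclusively. Severe AESCs are named in the same rule and are defined in Definitions of Terms by potential relation to an allogeneic reaction, not by the 8.1.2 grade.

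A reader might also take Table 11's 27.0% as the share of patients who would fall in the missing category. That does not follow. The figure covers non-serious events with the autologous product and/or its procedure. Possibly related describes what the table summarises, and nothing shows that these events were graded possible or on what scale.

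Finally, one could say that mapping the existing grades is enough and a new one is a matter of preference. A mapping would settle the rules for tables and imputation, but not the identification problem in step 2 of the working.

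**Conclusion.** The point holds as a defect in a data-collection instrument together with a missing definition. Both statements of the scale lack the grade that matches the question asked, so possible events are merged irrecoverably with likely or unlikely ones. No visible text links the grades to potentially related or treatment-related.

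The size is not estimable from the documents. The ambiguity in the related-AE count is bounded by P, the number of possible events among at most 32 treated patients, and P is not given. The conclusion assumes that some events will be judged possible but not likely, which is plausible given the overlap of immune and procedural signs. It also assumes that no mapping exists in redacted text or in a SAP beyond what is visible; 10.5.7.2 defers detailed safety methods to the SAP. The change is worth making because it is cheap and the information cannot be rebuilt later.

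**What to change.** 1. Add a *Possible* grade between *Likely* and *Unlikely* in 8.1.2 and on the AE and SAE forms, and align the sentence in 8.3.1.2.
2. State in the protocol or SAP which grades count as related for the tables in 10.5.7.1 and for the WOCF/LOCF choice in 10.8. Unknown/not assessable should not be treated as unrelated by default.
3. Reconcile 8.1.2, 8.3.1.2, 8.2.4 and 10.9 so that the term governing the SMC review and block release is expressed on the scale. Which grades should hold or release a block is for the sponsor and the SMC; no rule is proposed here.

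Events already recorded need not be re-graded. In an open study that would be done with outcomes known and could introduce bias of its own.

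The cost is one CRF option, a short mapping statement, and possibly a slightly higher reported related-AE rate.
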